**I. Hypotheses and Specific Aims:**

Developing effective reproductive health interventions for women in treatment for substance use disorders has tremendous potential to improve the health of women and children. In the US nearly half (51%) of all pregnancies are unplanned (L. B. Finer & Zolna, 2014). A recent study of pregnant women entering opioid medication-assisted treatment found much higher proportions – 86% described their current pregnancy as being unintended and about a third of these pregnancies were described as being unwanted (Heil et al., 2011). Women with unintended pregnancies had higher rates of recent substance use and almost all (90%) had a history of prior treatment for substance use disorders. Thus, substance use treatment programs are promising venues for addressing contraception.

Although there is a paucity of interventions specifically focused on preventing unintended pregnancies among women with substance use disorders, prior research from the addiction treatment and reproductive health fields provides relevant guidance for selecting key intervention elements. The addiction treatment field has an established history of using peers to support recovery (White, 2004). Peers have been used in effective HIV prevention interventions with vulnerable and hard to reach populations (Kelly, 2004; Kelly et al., 1991) and with adolescents (Brindis, Geierstanger, Wilcox, McCarter, & Hubbard, 2005; Key, Gebregziabher, Marsh, & O'Rourke, 2008). Involving individuals with similar life experiences may foster trust in intervention programs and increase sensitivity to the perspectives of the individuals in the target population. Thus, we propose to involve peers in a contraceptive and reproductive health education among women in treatment settings.

Long-acting reversible contraceptive (LARC) methods, such as intrauterine devices and subdermal implants, are considered the most effective method of reducing rates of unintended pregnancies (American College of Obstetricians and Gynecologists Committee Opinion no 450, 2009; Trussel et al., 2009; Trussell, 2012). Yet little is known about LARC use among women who use substances. LARCs are likely to be acceptable among this population as national data indicate similar rates of LARC use among low income women (6.1%) and women on Medicaid (6.7%) compared to all women using contraception (5.6%) (Kavanaugh, Jerman, Hubacher, Kost, & Finer, 2011). Furthermore, a recent Colorado Initiative promoting LARC use found an increase in uptake (5%-19%) among young low-income women (Ricketts, Klingler, & Schwalberg, 2014) and another

study among women seeking contraception found high rates (70%) of LARC acceptance (Mestad et al., 2011).

This study proposes to draw upon behavioral theory and prior evidence-based interventions to develop an innovative brief peer-led intervention to increase LARC uptake for women of child-bearing age entering opioid medication-assisted treatment (OMAT). The Health Belief Model HBM (Rosenstock, 1974) will be used to guide intervention development. HBM is a multidimensional social cognitive framework that focuses on modifiable factors related to decision making and behavior and was recently operationalized specifically to support current contraceptive research and practice. (Hall, 2012).

The study will utilize a mixed methods approach and involve two phases. The first phase will be a formative evaluation that will include individual qualitative interviews and focus groups with women in OMAT; the resulting information will be coupled with prior evidence and theory to develop the structure of the intervention. The second phase will involve the piloting and implementation of a peer-led sexual health intervention with women in OMAT. Women (150) will be recruited from two clinic sites and randomized to usual care (N=80) or intervention (N=80).

**Aim 1.** To develop a brief theory-based peer-led intervention to prevent unintended pregnancies among women entering opioid medication-assisted treatment.

- a. Conduct up to 30 individual qualitative interviews to better understand: pregnancy desires/motivation and perceived susceptibility and severity; and contraceptive knowledge, perceived benefits/barriers, self-efficacy, social norms, behaviors and access to contraception and family planning services, especially related to LARCs.
- b. Combine information from the qualitative interviews with HBM theory and results of prior research to specify the peer-led intervention.
- c. Assess acceptability and feasibility of the intervention in two focus groups and refine.
- d. Pilot the intervention with 10 women and finalize.

**Aim 2.** To assess acceptability, feasibility and the initial efficacy of the behavioral intervention ( $n=75$ ) as compared to usual care in substance use treatment ( $n=75$ ).

**Aim 3.** To conduct exploratory analyses to identify HBM constructs that are the most influential on LARC use

**Hypothesis 1.** Participants randomized to the intervention will be more likely to follow-up with a family planning clinic visit.

**Hypothesis 2.** Participants randomized to the intervention will be more likely to initiate Long Acting Reversible Contraceptive (LARCS) methods.

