Information from the individual interviews will be combined with evidence from the literature to further specify the intervention. The intervention will then be operationalized by creating a manual as well as a detailed outline that will be used to solicit feedback in the focus groups. We will then conduct two focus groups with the primary aim of obtaining women's feedback on the intervention and their thoughts on the most important aspects of HBM as related to contraception decision making and behavior. Focus groups are a strong addition to our formative methods, as they provide a cost-effective method of collecting information and a social forum to further evaluate the intervention. The social forum helps to identify salient issues and weed out extreme views that may have been obtained in the individual interviews (Agar & MacDonald, 1995). It also allows participants to interact and respond to each other's ideas. This synergy will provide valuable information in further refining the intervention. After each focus group, suggestions will be reviewed and needed modifications will be made to the intervention content and structure. Additionally, during this time, processes will be explored and put in place for referral to family planning services.

**B. Phase II.** We will then recruit 160 women in OMAT to participate in this phase of the study. Quantitative study data will be collected through participant surveys at baseline, 3 months, and 6 months follow-up. We will collect baseline data on a tablet, and 3 and 6 months follow-up using RedCap. A copy of this survey is included in this application and the content is as follows:

- Demographic data: Age, religion, sexuality, living situation, partnership status, previous pregnancies length of time in treatment and number of unique episodes
- Psychosocial: Knowledge of contraceptive methods and pregnancy risk; stage of change and level of motivation to prevent unintended pregnancies, attitudes towards different contraceptive methods, self-efficacy regarding condom and birth control use, ability to engage in preventive behaviors, partner communication, pregnancy desires
- Current behavior: In last 30 days and most recent: number of partners, number of vaginal sex acts, times used contraceptives, times used condoms, partner perceptions of contraceptives and condoms, risk behaviors.

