the completion of the interview, the researcher will retrieve the tablet, copy the interview to a secure Denver Health network drive, and erase the file from the tablet. The researcher will then pay the participant for her time. The three and six month interview will be done online using RedCap, a secure software that is regularly used in research. A spreadsheet will be developed to manage all aspects of study data. After the baseline interview, the research assistant will assign participants into study groups based on pre-defined randomization based on study ID.

For the first 10 patients recruited, we will ask them to provide feedback on the baseline survey and intervention and this information will be used to further refine the study survey and intervention. Depending upon the changes made, data from these initial participants may be excluded from the final analyses.

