Many of the variables will be either summary index scores or latent variables that assess the psychological, behavioral and biological constructs of interest. For example knowledge will be a summary score representing the number of variables the participant correctly endorsed, while motivation will be a mean score across multiple variables representing the underlying latent construct. The variable related to use of LARCs will be a dichotomous variable representing current use or no current use of a LARC method (IUD or Implanon), as will attending a family planning visit during the study period.

Separate analyses will be conducted for each of the hypothesis to understand differential change over time. This includes looking at change scores as well as analysis of variance. The expectations for hypotheses 1 and 2 are that they will significantly increase in the intervention group. Differences will be assessed from baseline to follow-up period for each analysis.

Additional regression analyses will be conducted to identify significant predictors of differential change over time in birth control method and family planning visit. This analysis will determine if the intervention condition is a significant predictor of change. The regressions will account for any important statistically significant differences between groups at baseline. These differences may include variables pertaining to demographics, psychosocial factors, and behavioral variables. Generalized estimated equations (GEE) will be used to account for the within-subject correlation of repeated measures by individual patients. Group designations for the outcome analyses will adhere to the intention to treat threshold. All Statistical analyses will be performed using SAS (version 9.1 or later, SAS Institute Inc, Cary, NC) software.

*Engagement variables.* We will collect and analyze engagement with the PN and attendance to each session. These analyses will be used to assess intervention fidelity and to describe the amount of intervention each participant received to understand acceptability of the intervention as well as the relationship of intervention dose to study outcomes. These data will include, intervention activities covered and descriptive information such as the number of sessions attended, and the number of interactions with

the PN.

We will also record intervention sessions with the PN to determine the fidelity in which each session has been administered.

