**Study Statistical Power.** Power analyses were done to assess the minimum detectable improvement needed for LARC uptake. A sample of 75 per group, using ITT approaches and assuming outcome if failure (dichotomous only) for patients who do not respond to follow-up surveys will provide 80% power to detect 23% difference between usual care and intervention patients on dichotomous outcomes, assuming an average success rate of 50% for maximum variability. For continuous outcomes, a follow-up sample size of 60 per group will provide 80% power to detect a .55 SD difference between usual care and intervention patients, or a medium linear effect over time (correlational structure CS with  $\rho=.5$ ).

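### The Phase II sample size is given as 150 and as 160, and the plan does not say whether the first ten women, whose data may be dropped, are randomised

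*Combined protocol and SAP*

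**What the plan says.** Four places in the combined protocol and SAP give the Phase II size:

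- Section I, overview before the aims: "Women (150) will be recruited from two clinic sites and randomized to usual care (N=80) or intervention (N=80".
- Section I, Aim 2: "initial efficacy of the behavioral intervention ( $n=75$ ) as compared to usual care in substance use treatment ( $n=75".
- Section IV.B, Phase II: "We will then recruit 160 women in OMAT to participate in this phase of the study".
- Section IV.F, Study Statistical Power: "A sample of 75 per group, using ITT approaches".

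On assignment, Section IV.C (Phase II Efficacy Evaluation) says that after the baseline interview "the research assistant will assign participants into study groups based on pre-defined randomization based on study ID". The next paragraph asks the first ten recruits to comment on the survey and the intervention, and adds: "Depending upon the changes made, data from these initial participants may be excluded from the final analyses".

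On the analysis set, Section IV.F says: "Group designations for the outcome analyses will adhere to the intention to treat threshold". The power statement counts women who do not answer follow-up surveys as failures on dichotomous outcomes.

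On the pilot, Aim 1d and the opening of Section IV.C place a ten-woman pilot before the randomised phase. The Section I overview places it within Phase II: "The second phase will involve the piloting and implementation of a peer-led sexual health intervention with women in OMAT".

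**The concern.** The sentence in the Specific Aims cannot be right as it stands, because it randomises more women than it recruits. Losses between recruitment and randomisation would work in the other direction. The other three statements split between 150 and 160, so a reader cannot tell when recruitment stops or what the planned denominator is.

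The clause on the first ten women adds a second uncertainty of the same size. It does not say which changes count, who decides, when, or whether the women would be replaced. The assignment rule makes no exception for them. If they are randomised, women could be removed after assignment by a decision that no rule governs. If they are not, the plan contains a pilot group that it does not name. The final analysis set could include or omit them, and either choice could claim support from the text.

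**Working it through.** **Totals.**

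- Specific Aims: 150 stated, 80 + 80 = 160 by arm.
- Aim 2 and power statement: 75 + 75 = 150.
- Section IV.B: 160 recruited.
- Difference: 160 − 150 = 10 women, which is 10/160 = 6.3% or 10/150 = 6.7%.
- 160 − 10 = 150 = 2 × 75, so a ten-woman pilot would reconcile 160 with 75 per group. It would not reconcile the sentence that randomises 80 and 80.

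**Inputs for power.** The power statement gives 75 per group, 80% power, a 23-point difference and a mean success rate of one half, taken here as 38.5% v 61.5%. Section IV.F sets an error rate of 0.05 for each planned comparison. A two-sided test is assumed, as the plan does not say.

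**Formula.** Pooled two-proportion test without continuity correction, n per arm:

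power = Φ{ [d√n − 1.96·√(2p̄q̄)] / √(p₁q₁ + p₂q₂) }

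Here d = 0.23, √(2p̄q̄) = √0.5 = 0.7071, and √(p₁q₁ + p₂q₂) = √(2 × 0.385 × 0.615) = 0.6882.

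**The plan's own figure.** n = 75: (0.23 × 8.660 − 1.386)/0.6882 = 0.606/0.6882 = 0.881, so power is 81.1%. Solving for n at 80% power gives 73 per group. The stated 75 per group is reproduced.

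**The other readings.** For unequal arms, the same test uses the standard errors based on 1/n₁ + 1/n₂.

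| Reading | Arms | Power for 23 points |
|---|---|---|
| 160 randomised, all analysed | 80 v 80 | 83.5% |
| 150 randomised, all analysed | 75 v 75 | 81.1% |
| 160 randomised, 10 dropped evenly | 75 v 75 | 81.1% |
| 160 randomised, 10 dropped from one arm | 80 v 70 | 80.9% |
| 150 randomised, 10 dropped evenly | 70 v 70 | 78.3% |
| 150 randomised, 10 dropped from one arm | 75 v 65 | 78.1% |

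The whole range is 83.5 − 78.1 = 5.4 points. Within a fixed total, dropping ten costs at most about 3 points (81.1 − 78.1). The detectable difference at 80% power is 22.0 points at 80 per arm, 22.7 at 75 and 23.5 at 70.

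**Status of the first ten.** Two parts of Section IV.C suggest they are randomised: the assignment rule has no exception, and the second phase is described as randomising its subjects. One part suggests they are not: they are asked about the intervention, which usual-care women do not receive. The text does not settle it.

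**The case against.** The strongest defence is that the ten women are simply the pilot of Aim 1d. The request for feedback on the intervention fits that, and so does 160 = 10 + 150. The exclusion is limited to ten named-in-advance recruits and depends on changes to the survey or intervention, not on outcomes. The sentence on group designations concerns the arm in which a woman is analysed and does not expressly define who is analysed. The intention-to-treat wording in the power statement is tied to survey non-response. A randomisation list for 160 also serves 150.

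Much of this stands. A reader might infer that the plan already breaches intention to treat. The documents do not show that: the conflict arises only if the ten are randomised, and nothing suggests selection on outcome. A reader might also infer that the randomisation list would fail, but no blocking scheme is described that a difference of ten would upset.

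What the defence does not remove is that the pilot explanation is nowhere stated, that the Specific Aims contradict it by randomising 80 and 80, and that the exclusion has no criterion or timing.

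**Conclusion.** The inconsistency is real and should be corrected. The plan gives two totals ten women apart, one sentence contradicts itself, and the status of the first ten recruits is undefined. Whether the clause permits post-randomisation exclusion depends on that status, so this part of the point is conditional.

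A reader might conclude that the trial is underpowered. The documents do not support this. The power statement reproduces at 75 per group, and power falls below the stated 80% only if 150 are randomised and ten are then dropped (about 78%). These figures assume a two-sided 0.05 test, equal allocation and rates centred on 50%. If the 23 points were instead read as 50% v 73%, even 70 per arm would give 80.5%. The case therefore rests on a single, fixed sample size and analysis set more than on lost power.

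**What to change.** Choose one option.

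**Option A.** State that 160 women are recruited: ten designated in advance as a non-randomised pilot and always left out of the efficacy analysis, plus 150 randomised 75:75. Say whether these ten are the Aim 1d pilot. Change 80 and 80 in the Specific Aims to 75 and 75. Keep 160 in Section IV.B as the recruited total, and leave the power statement as it is. Replace the optional exclusion in Section IV.C with this fixed rule.

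**Option B.** Randomise 160 as 80:80. Change 150 in the Specific Aims, and 75 per group in Aim 2 and the power statement, to match. Delete the sentence in Section IV.C that allows the first ten to be excluded, and analyse every randomised woman. The stated 80% power for 23 points is then met (83.5%); restating it as 22 points is optional.

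Under either option, make the Section I overview agree with Aim 1d and the opening of Section IV.C on which phase holds the pilot.

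The cost is wording only. Option A leaves the number recruited at 160 and the power statement unchanged.

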## **II. Background and Significance:**

***Unintended pregnancies and public health.*** Reducing unintended pregnancies is an important public health concern and is a national health goal that has been identified by the U.S. Department of Health and Human Services', *Healthy People 2020* campaign. In 2008, about half (51%) of the pregnancies in the US were unintended (L. B. Finer & Zolna, 2014). Additionally, disparities in unintended pregnancy rates exist for low income women, women with less than a high school education and minority women (L. B. Finer & Zolna, 2014). Unintended pregnancies have both financial and public health impacts. It is estimated that unintended pregnancies cost US taxpayers approximately \$11 billion

dollars a year (Sonfield, Kost, Gold, & Finer, 2011). This is most likely a conservative estimate as costs were limited to public insurance costs for pregnancy and first-year infant care. Additionally, unintended pregnancies can lead to unintended childbearing, which is associated with adverse maternal behaviors before pregnancy is known, such as delayed or inadequate prenatal care, and/or substance use during pregnancy (L. B. Finer & Henshaw, 2006).

***Unintended pregnancies in women who use substances.*** Studies suggest that unintended pregnancy rates are much higher among women with substance use disorders than in the general population. A seminal study of the reproductive health needs of women with opioid dependence demonstrated higher rates of lifetime pregnancies and abortions compared to national averages, suggesting that many pregnancies in this group were unintended (Armstrong, Kennedy, Kline, & Tunstall, 1999). A small study of pregnant women in methadone maintenance found that 67% did not plan their current pregnancy (Selwyn et al., 1989). In a more recent multi-site study of 946 pregnant women in treatment for opioid use disorders, 86% reported that their current pregnancy was unintended, of which 40% reported it was mistimed, 31% reported it was unwanted and 30% reported being ambivalent (Heil, et al., 2011). These numbers underscore the importance of targeting this population and developing effective interventions that bridge the gap between pregnancy desire and contraceptive behavior. Additionally, women with unintentional pregnancies had significantly more substance use in the past 30 days compared with women with intentional pregnancies. Women often do not find out they are pregnant until after the fourth week of pregnancy, well into a critical period for fetal development (Floyd, Decoufle, & Hungerford, 1999). Thus, women with substance use disorders, even those in recovery, may be at a much higher risk of having a substance-exposed pregnancy especially if the pregnancy is unintended. Continued substance use during pregnancy has been associated with immediate and long-term effects on exposed children ranging from premature delivery and low birth weight to developmental deficits that affect behavior and cognitions over the life course (NIDA., 2011). Additionally, the recent national increases in neonatal abstinence syndrome and antepartum maternal opioid use (Patrick et al., 2012), suggest that contraceptive interventions are particularly important for women with opioid use disorders.

***Substance use treatment settings: a missed opportunity for prevention of unintended pregnancies.*** Reproductive health is an important issue among women in treatment for substance use disorders but is often not adequately addressed (Armstrong, Kenen, & Samost, 1991). While most treatment venues include sexually transmitted infection (STI) testing and education, most do not include a contraception focus or adequate connection to reproductive health services. In Heil's (2011) study with pregnant opioid-dependent women, almost all of the women (90%) in the study had a history of prior treatment for substance use disorders with an average of three or more treatment episodes. This finding strongly supports the idea that treatment programs are a vital setting for engaging at-risk women and empowering them to take control over their reproductive health. Treatment is a time of change and self-evaluation. Integrating a peer-led contraception intervention into this setting may provide women with additional resources that contribute to greater self-efficacy, empowerment and future stability in their lives and that in turn positively support their recovery.

***The potential role of peers in prevention for women with addiction.*** Within the mental health and addiction fields, there is a history of using peer-based recovery support groups and recovered/recovering peers in service and support roles (White, 2004). Peers have also been used in health promotion and HIV prevention with hard to engage populations (Kelly, 2004; Kelly, et al., 1991) and adolescents (Brindis, et al., 2005;

Jemmott, Jemmott, & Fong, 1998; Key, et al., 2008; Siegel, Aten, Roghmann, & Enaharo, 1998). The definitional clarity and diversity of interventions that fall under the umbrella of “peer education” has hindered the evaluation of the value of this method (Shiner, 1999). In a study among adolescents receiving family planning services at a community health clinic, patients whose clinic services were augmented with a peer intervention were more likely to report consistent and effective contraceptive use at follow-up (Brindis, et al., 2005). However, in a sexual health school-based study that utilized peer-educators in group settings, differences were not found between students in the intervention and control groups (Mason-Jones, Mathews, & Flisher, 2011). The proposed study will rigorously operationalize and measure a peer education intervention that will include peers not only in the delivery of the intervention but also in the development of the intervention. Peer education has been more heavily promoted in projects working with vulnerable and hard to reach populations. The premise is that individuals may be more likely to personalize health messages if they are delivered by someone who understands and is facing similar concerns and pressures. Using peers who have experienced past substance use problems, provides participants with successful real-life role models. This may be particularly helpful in developing trust, ensuring the intervention incorporates the cultural context surrounding substance use, and empowering substance-using women to engage and take control over their reproductive health.

***The opportunity provided by increased availability of Long-Acting Reversible Contraceptives.*** LARCS which include intrauterine devices (Mirena®, ParaGard®, Skyla®) and subdermal implants (Nexplanon®), are considered to be safe, cost-effective methods to reduce the rates of unintended pregnancies (American College of Obstetricians and Gynecologists Committee Opinion no 450, 2009; Trussel, et al., 2009; Trussell, 2012). By requiring little user participation to avoid pregnancy, their failure rates are very low (less than 1%) (Hatcher et al., 2007; Kost, Singh, Vaughan, Trussell, & Bankole, 2008; Trussel, et al., 2009). Rates of LARC use have continued to increase over the last decade in the US (L. Finer, Jerman, & Kavanaugh, 2012) and LARCs appear to be acceptable methods of contraception among low-income women and women on Medicaid (Kavanaugh, et al., 2011) A recent Colorado Family Planning Initiative focused on increasing LARC use among young low-income women observed a population increase in LARC use from 5% to 19% as well as a decrease in observed fertility rates, high-risk births, abortion rates and infant enrollment in WIC (Ricketts, et al., 2014). Another recent project promoting LARC use among women seeking contraception found that 70% of the women chose a LARC method as compared to a non-LARC method when the barrier of cost was removed and when counseling on the effectiveness of LARC methods was provided (Mestad, et al., 2011). Implementation of the Affordable Care Act and greater Medicaid coverage decreases financial barriers in accessing these methods. Women entering treatment often have multiple life issues to address and providing contraceptive options, especially LARC methods, may be particularly attractive and effective in reducing unintended pregnancies.

***Theory to inform the study.*** Recent contraceptive interventions have not relied as heavily on theory as HIV prevention interventions. In a review of theory-based contraception interventions, the most heavily used theoretical basis was social cognitive theory (SCT) (Lopez, Tolley, Grimes, Chen, & Stockton, 2013). HBM is a social cognitive framework that applies a multidimensional approach to decision making and heavily relies on modifiable cognitive factors (Rosenstock, 1974). HBM will be used to guide the overall framework for operationalizing intervention content and measurement. HBM consists of 6 constructs that influence individual health related decision making and behaviors: perceived susceptibility (chance of getting a condition); perceived severity (seriousness of

the condition and its consequences); perceived benefits (ability of the preventive behavior to reduce risk); perceived barriers (the cost of the preventive behavior); cues to action (internal and external signals that trigger action) and self-efficacy (confidence in one's ability to take action). Self-efficacy, a component of HBM and an essential construct in Social Cognitive Theory (Bandura, 1986), has been utilized in many health studies and has been found to be an important predictor of safer sex behaviors (Brien, Thombs, Mahoney, & Wallnau, 1994; Goldman & Harlow, 1993; Longshore, Stein, & Chin, 2006; O'Leary, Goodhart, Jemmott, & Boccher-Lattimore, 1992; Sikkema et al., 1995; Wulfert & Wan, 1993). Thus, contraceptive self-efficacy will be a specific focus in the intervention. A recent conceptual review of primary research articles applying HBM to family planning, consolidated past work to specify a contraception specific HBM framework to be used to guide future research, measurement and practice (Hall, 2012).

Motivational Interviewing (MI) is an empirically supported intervention method and style that is effective in a number of health issues within short time frames (Lundahl et al., 2013; Martins & McNeil, 2009). MI has been extensively used in the addiction field and has been shown to be effective in brief interventions targeting alcohol use and contraception behaviors (Ingersoll, Ceperich, Hettema, Farrell-Carnahan, & Penberthy, 2013). It is a directive but client-centered approach focused on increasing patient motivation to change behaviors through exploring and resolving ambivalence (Miller & Rollnick, 2002). Structured elements of MI will be incorporated into the intervention, specifically providing personalized feedback on current contraception methods, developing discrepancy between contraception behaviors and pregnancy intentions, and goal setting.

**Summary.** Gaining a better understanding of the contraceptive and reproductive health needs of women struggling with addiction is an important public health issue. This study will develop a brief peer-led intervention that can be integrated into the substance use treatment setting and may prove to be a significant contribution to the public health effort of both reducing unintended and substance-exposed pregnancies. Additionally, empowering women to take control over their reproductive health may also create more long-term stability in their lives and positively support their recovery.

